1.1.2 Existence of a Dynamic Equilibrium between Brain and Plasma $A\beta$

Both tau protein and $A\beta_{1-42}$ peptide are able to cross the BBB. $A\beta$ is normally detectable in plasma, though the levels are 100-fold lower than in CSF, suggesting that $A\beta_{1-42}$ is predominantly produced in the CNS³. Earlier studies in both animal models and humans have detected the presence of a bidirectional flow of $A\beta$ peptide between the CSF compartment and plasma¹¹⁻¹⁹, with involvement of the subependymal and choroid plexus capillaries³. In some cases, it has even been shown that the elimination half-life of $A\beta$ between CSF and plasma is about 30 minutes^{11,18}. On the other hand, some researchers have demonstrated that the plasma levels of $A\beta$ decrease as the deposits of the latter within the brain increase^{20,21}, while other investigators have reported high plasma levels of $A\beta$ both after active immunization with $A\beta$ ⁷ and after passive immunization with anti- $A\beta$ antibodies^{8,22}.

Taken globally, the above data, i.e., bidirectional flow and deliberate imbalance of the flow in one or the other direction, supports the existence of a dynamic equilibrium between plasma

and brain A β . In this context, Sigurdsson et al.⁹, among other authors⁴, have suggested intervention upon A β pertaining to the plasma compartment, to induce a reduction in the peptide and thus alter the aforementioned equilibrium. Specifically, Sigurdsson et al. recommend the adoption of an A β peripheral clearance strategy based on the use of IgM type antibodies. This strategy would have the advantage of sequestering peripheral A β , with preservation of the brain tissue, since IgM is practically undetectable in CSF⁹. In this way, the above mentioned authors consider that it would be possible to avoid adverse events directly produced by interaction of the antibodies with the brain tissue, as in the documented cases of encephalitis that recently have made it necessary to prematurely interrupt a phase II clinical trial testing active immunization with A β ₁₋₄₂. Although the precise mechanism underlying this complication is not known, some investigators have demonstrated the existence of brain vascular microhemorrhages after passive immunization in animal studies^{23,24}.

Other investigators have taken a step further. Likewise based on the dynamic equilibrium principle, they have demonstrated that peripheral sequestering of plasma A β using substances other than antibodies - though with high affinity for the peptide - is able to reduce both A β in CSF and in the brain tissues. Specifically, Matsuoka et al.²⁵ demonstrated the above using two different substances, gelsolin and GM1 ganglioside. Neither of these two substances appeared to any appreciable degree in CSF, and both produced the desired imbalance in both CSF and brain A β . A relevant observation is the fact that probably encouraged by the expectations raised by these results, the mentioned investigators requested a patent of the described procedure, in the name of the investigators themselves for the United States and in the name of the New York State Office of Mental Health for the rest of the world (WO 03/051374 A3).

Recently, Cleary et al.¹⁰ have demonstrated that the soluble oligomers of A β that go on to form part of the amyloid plaques are already neurotoxic before the fibrillar forms are produced; as a result, they would play a relevant role in the early forms of AD.

1.1.3 The Role of Plasma exchange with Albutein[®] 5% in Alzheimer's disease

The amyloid precursor protein (APP) and A β itself are secreted during normal cell metabolism, with small amounts of both being found in CSF and plasma. In both compartments, A β is associated to proteins³ that may contribute to maintain the solubility of A β . One such protein is albumin, which is the most abundant protein in both blood and CSF. In this sense, albumin is able to bind to and transport a range of small molecules, including peptides and drugs. Only 40% of body albumin is contained in plasma; the remaining 60% is found in the extracellular fluids. The great majority of A β circulating in blood (89%) is bound to albumin in 1:1 proportion⁴, and only 5% is bound to high density lipoproteins (apoenzyme E, ApoE and apoenzyme J, ApoJ)^{26,27}. It has been shown that albumin is one of the most important binding proteins, and one of the most potent inhibitors of A β polymerization⁴.

Plasma exchange is a process used to eliminate patient plasma and replace it with another solution maintaining normal volemia and osmotic balance. To this effect, albumin or other colloids have been used, as well as fresh frozen plasma (FFP) and crystalloids. The purpose of this procedure is to eliminate toxic substances from patient plasma, such as: autoantibodies, alloantibodies, immune complexes, proteins, or toxins²⁸. The clinical efficacy of plasma exchange depends on many factors, including the volume exchanged, the number and frequency of sessions, the nature of the replacing solution, and the separation technique employed. Data obtained in animal studies have shown human albumin to be neuroprotective

in models of acute ischemic infarction, improving neuron function and reducing both infarct volume and brain edema²⁹.

Plasma exchange is widely used in treatment of different pathologies. Specifically, the procedure has been applied to the following disorders: Guillain-Barré syndrome (acute treatment)³⁰, multiple sclerosis (chronic treatment)²⁸, inflammatory demyelinating polyradiculoneuropathy³¹, acute inflammatory demyelinating disease of the CNS³² and other peripheral neurological alterations³³. Since 2004, the Banc de Sang i Teixits (BST) (Barcelona, Spain) has carried out 401 plasma exchange procedures and over 5000 aphereses. In comparison with this study, all perform a greater number of replacements, or alternatively the volume replaced is greater or the sessions are performed more frequently.

On the other hand, in the clinical investigation of AD, methods more aggressive than plasma exchange have been used, such as ventriculoperitoneal shunting, which is a method involving implantation of a catheter connecting the brain ventricles with the peritoneal space for the drainage of CSF^{34,35}.

Albutein[®] 5% has been marketed in USA since 1978, though albumin had already been in use in different countries since the 1940s. Since then the product has been continuously used in application to different clinical conditions, and is even employed as placebo in many clinical trials.

1.1.4 Previous Clinical Studies of Plasma exchange with Albutein[®] 5% in Alzheimer's disease

In order to evaluate the effects of plasma exchange with Albutein[®] 5% in patients with mild to moderate AD, Grifols S.A. in 2005 started a pilot study directed by [name] of the Service of Neurology of Vall d'Hebron Hospital and of the Fundació ACE in Barcelona, Spain. Ten patients were recruited, of which seven were subjected to plasma exchange, two received no treatment, and one was removed from the study upon personal request. Of the seven subjects treated, three underwent five plasma exchanges, two patients received four exchanges, and two underwent three exchanges during a period of three weeks. The participants were subsequently followed-up on for a period of 12 months.

The most important variables recorded were the following:

- changes in the levels of A β ₁₋₄₀ and A β ₁₋₄₂ in plasma,
- changes in the levels of A β ₁₋₄₀ and A β ₁₋₄₂ in CSF,
- changes in the neuropsychological test results (MMSE and ADAS-Cog), and
- changes in the neuroimaging studies (MRI and SPECT).

Results showed a consistent pattern of A β mobilization as well as a trend to stabilization in the MMSE and ADAS-Cog⁶⁵.

Based on these results a phase II clinical trial was conducted in 4 sites, 2 in Spain and 2 in the USA, with 42 patients recruited. The trial was a randomized, controlled, single-blind study in which 3 different plasma-exchange schedules were assessed: 1) 6 plasma exchanges in 3 weeks, 2) 6 plasma exchanges in 6 weeks and 3) 6 plasma exchanges in 12 weeks. Therefore, patients that completed all cycles underwent a total of 18 plasma exchanges. The control group underwent sham (simulations) procedures that mimicked the actual procedures. Interim results have recently been published and they show a consistent pattern of A β mobilization as well as an improvement of the MMSE and ADAS-Cog of 2.5 and 5.5 points, respectively, at 9 months of follow-up. In terms of A β mobilization, the schedule of 6 plasma exchanges in 6 weeks seemed to be more effective than 6 plasma exchanges in 12 weeks and of similar

effectiveness as 6 plasma exchanges in 3 weeks⁶⁵. Thus, 6 plasma exchanges in six weeks were selected as a potential load treatment for future trials.

1.1.5 The role of intravenous immunoglobulin in Alzheimer's disease

In 2004 IVIG was used for the first time in a pilot study of Alzheimer's disease⁶⁶. The study included 5 patients and the results showed an improvement in the ADAS-Cog scale but not in the MMSE. The first randomized clinical trial of IVIG in Alzheimer's disease was performed on 8 patients⁶⁷ during a follow up of 18 months and the results showed plasma A β mobilization after each IVIG administration as well as a trend to cognitive stabilization. A second randomized clinical trial involving 24 patients has been completed⁶⁸ and the preliminary results presented in the *American Academy of Neurology 2010* meeting showed a statistical significant improvement of 6 points in the ADAS-Cog scores. In addition, a phase III study involving 360 patients is currently ongoing⁶⁹.

On the other hand, Grifols S.A. has conducted a pilot study of IVIG in 4 patients that had previously participated in the pilot study mentioned in section 1.1.4 and the preliminary results showed a similar pattern of plasma A β mobilization as compared to that observed in the plasma-exchange study.

1.1.6 Potential role of a combination of plasma exchange with Albutein[®] with Flebogamma[®] DIF

Taking into consideration the results of the clinical studies mentioned above, it can be concluded that both approaches, plasma exchange with albumin and IVIG infusion, act on the peripheral A β pool, as seen through the plasma A β mobilization observed, and that both approaches show a trend to cognitive improvement. Therefore, it seems reasonable to search for a synergy between the two treatments using lower doses of each of them which will also imply less concern about safety issues. In fact, for selected neurologic diseases, this combination approach has already been used^{70, 71}.

We propose here a combination of monthly low-volume plasma exchanges (similar to regular plasma donation plasmaphereses) with IVIG every four months. Previously, there will be a load treatment with six plasma exchanges in six weeks to assure the baseline results obtained in previous studies. Albutein[®] and Flebogamma[®] DIF, two approved products, will be used as albumin and IVIG, respectively.

2. STUDY PURPOSE AND OBJECTIVES

Primary objective

The primary objective of this study is to evaluate the changes in the cognitive, functional, behavioral and global domains based on the different applicable psychometric batteries and scales.

Secondary objectives:

The secondary objectives of this study are:

- To determine the changes in the concentration of beta-amyloid peptide in plasma and cerebrospinal fluid (CSF) in the treatment group of patients with Alzheimer's disease (AD)
- To evaluate the structural changes in volume of the hippocampus, posterior cingulate area, and other associated areas based on neuroimaging studies with MRI (variations versus baseline).

- To determine functional brain changes through FDG-PET (fluorodeoxyglucose-PET).
- To determine whether plasma exchange with human albumin combined with IVIG is safe, taking into account the following factors:
 - Type, severity and frequency of adverse reactions during and after the procedure and infusions.
 - Changes in vital signs and clinically relevant changes, according to the laboratory test findings.
 - Control of episodes of cerebrovascular accidents with MRI.

3. INVESTIGATIONAL PLAN

3.1 Global Study Design/Developmental Phase

The trial comprises a multicenter, randomized, controlled design. The subjects included in the study will be controlled from the first screening visit up to fourteen months after. Then, the maximum study duration for a given subject will be approximately one year and two months. There will be two weeks for screening and randomization of both groups (treatment and control). After these two weeks the treatment period will proceed as follows:

- One month and a half (six weeks) of intensive treatment with one full plasma exchange per week (all the three groups).
- Two of the three groups will follow 12 months of maintenance treatment with one low-volume plasma exchange every month combined with IVIG every 4 months administered at the end of the corresponding plasmapheresis instead of albumin (that is, 9 plasmaphereses with Albumin replacement and 3 plasmaphereses with IVIG replacement). During this year patients will follow one of the two different pre-allocated treatment arms: 1) with the doses of albumin and IVIG needed to replace those removed during the plasmapheresis, 2) with half of the doses of albumin and IVIG.
- One of the three groups will follow the same schedule as the above two groups but with half of the doses of albumin alone (without IVIG), that is, 12 plasmaphereses with half-dose albumin alone.

Patients in the control group will undergo sham procedures mimicking plasmaphereses but with neither fluid exchange nor albumin or IVIG administration (**See Appendix 8**).

There will be sites in Spain and USA.

The site of the Coordinating Investigator (Fundació ACE/Hospital Vall d'Hebron, Barcelona, SPAIN) will be the first site to be included. The rest of the sites will be incorporated progressively after the first site. Several months can elapse between the inclusion of the Spanish sites and the rest of sites.

3.2 Randomization and Treatment Assignment

After the screening period, the subjects will be randomized to one of the 3 treatment groups or the control group according to a [1:1:1:1] scheme.

3.3 Type of Control

Control group: the subjects will be AD patients involving the same inclusion and exclusion criteria as the treated subjects but will undergo sham procedures mimicking plasmaphereses but with neither fluid exchange nor albumin or IVIG administration.

3.4 Blinding Techniques

The control group will be subjected to simulated full plasma exchanges through a non-invasive procedure. Specifically, the tip of a cut catheter will be stitched to an adhesive gauze dressing (acting as a “second skin”) which will be placed on the subclavicular or jugular region. Then, a second adhesive gauze will cover the one with the catheter tip stitched to it. The cut catheter will be of characteristics similar to the catheters used in the treatment group. Also simulated low-volume plasma exchanges will be performed. Likewise, these subjects will receive the same visits as the patients in the treatment group.

This study is blind for patients, caregivers and raters.

The study Sham manual guideline describes all the sham procedures throughout the study (Appendix 9).

3.5 Screening Period (Pre-Randomization or Pharmacological Washout)

There will be a two-week period for screening before the six weeks of intensive treatment. At the end of the screening period subjects will be randomized to one of the three treatment groups or to the sham group.

4. SELECTION OF STUDY POPULATION

4.1 Inclusion and Exclusion Criteria

4.1.1 Inclusion Criteria

In order to be eligible for participation in the trial, the patients must meet the following requirements:

1. Males or females between 55-85 years of age at the time of signing of the informed consent document.
2. A diagnosis of Alzheimer’s disease (NINCDS-ADRDA criterion), and MMSE score between ≥ 18 and ≤ 26 .
3. Current stable treatment with AchEIs and/or memantine for the previous three months.
4. The patient and a close relative or the legal representative must read the patient information sheet, agree to participation in the trial, and then sign the informed consent document (the patient personally and the close relative/legal representative).
5. The patient must be able to follow the study protocol, receive the treatment in the established time period, and continue during the follow-up interval.
6. A brain CAT or MRI study obtained in the 12 months prior to screening, showing the absence of cerebrovascular disease, should be available. Nevertheless, it is mandatory to use the MRI obtained during the screening period to rule out any cerebrovascular disease such as microhemorrhages, infarction, hematoma, stroke, meningioma or other finding that could affect patient safety.
7. A stable care taker must be available, and must attend the patient study visits.

4.1.2 Exclusion Criteria

Patients meeting any of the following criteria will not be able to participate in the trial:

1. Any contraindication for plasma exchange due to behavioral disorders or abnormal coagulation parameters, such as for example:
 - Hypocalcemia ($\text{Ca}^{++} < 8.7$ mg/dL).
 - Thrombocytopenia ($< 100,000/\mu\text{L}$).
 - Fibrinogen < 1.5 g/L.
 - Prothrombin time (Quick) $p < 60\%$ versus control (INR > 1.5).
 - Beta-blocker treatment and bradycardia $< 55/\text{min}$.
 - Treatment with ACEIs (increased risk of allergic reactions).
2. Hemoglobin < 10 g/dL
3. Difficult venous access precluding plasma exchange.
4. A history of frequent adverse reactions (serious or otherwise) to blood products.
5. Hypersensitivity to albumin or allergies to any of the components of Albutein[®] 5%.
6. History of immunoglobulin A (IgA) deficiency.
7. Known allergies to Flebogamma[®] DIF components such as sorbitol.
8. History of thromboembolic complications of intravenous immunoglobulins.
9. Plasma creatinine > 2 mg/dl.
10. Uncontrolled high blood pressure (systolic blood pressure of 160 mmHg or higher and/or diastolic blood pressure of 100 mmHg or higher despite regular treatment during the last 3 months).
11. Liver cirrhosis or any liver problem with GPT $> 2.5 \times \text{ULN}$, or bilirubin > 2 mg/dL.
12. Heart diseases as evidenced by myocardial infarction, severe or unstable angina, or heart failure (New York Heart Association Class II, III or IV) in the past 12 months.
13. Participation in other clinical trials, or the receipt of any other investigational drug in the three months prior to the start of the study.
14. Any condition complicating adherence to the study protocol (illness with less than one year of expected survival, known drugs or alcohol abuse, etc.).
15. Pregnant or nursing women or women not using effective contraceptive methods for at least one month after plasma exchange.
16. Fewer than six years of education (exclusion criteria under medical criterion).
17. Less than three months with stable treatment for behavioral disorders including insomnia.
18. Patients being treated with anticoagulants or antiplatelet therapy (antiaggregants) should not be recruited in the study.

4.2 Disease Diagnostic Criteria

Probable mild to moderate Alzheimer's disease, according to NINCDS-ADRDA criteria 2, with stable AChEI treatment and an MMSE score of ≥ 18 and ≤ 26 .

4.3 Planned Number of Subjects

A sample size of 312 subjects (78 per each of the 4 groups) will make it possible to detect with nearly 92% power for the first of the co-primary efficacy variable (the changes from baseline of the ADAS -Cog scores) a difference in the mean of 3 points between any of the treatment groups and the control group, assuming the common standard deviation (SD) to be 5.55 (according to the data obtained in the phase II study⁶⁵), with a level of significance of 5%. This same sample size provides over 98% power for second of the co-primary endpoint variables (the changes from baseline of the ADCS-ADL inventory scores) a difference in the mean of 6.69 points between any of the treatment groups and the control group, assuming the common standard deviation (SD) to be 10.0 (according to the data obtained in the phase II study), with a level of significance of 5%.

The study will have joint power for these co-primary endpoints of at least 90% ($0.92 \times 0.98 = 0.90$). The calculation makes the conservative assumption that these endpoints are independent. Since these endpoints may be positively correlated 90% should serve as a lower bound on power.

Assuming a global dropout rate of approximately 15%, the study would have to enroll 364 subjects to obtain 312 subjects for evaluation.

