| METHODOLOGY | A clinical trial comprised of 364 subjects with probable mild to moderate AD will be conducted primarily to determine whether short-term followed by long-term, low-volume plasma exchange with human albumin combined with IVIG is able to modify patient's cognitive, functional, behavioral |

| | | |
|--|---|------------------------|
| | 
and global domains. There will be 3 treatment groups and one control group. The subjects will be randomized in a 1:1:1:1 proportion.
 
After screening and randomization, treatment groups will proceed as follows:
 
 • One month and a half (6 weeks) of intensive treatment with one plasma exchange per week. All 3 treatment groups are the same during the intensive treatment phase. • Two of the three groups will follow 12 months of maintenance treatment with one low-volume plasma exchange every month combined with IVIG every 4 months administered at the end of the corresponding plasmapheresis instead of albumin (that is, 9 plasmaphereses with Albumin replacement and 3 plasmaphereses with IVIG replacement). During this year patients will follow one of the two different pre-allocated treatment arms: 1) with the doses of albumin and IVIG needed to replace those removed during the plasmapheresis, 2) with half of the doses of albumin and IVIG, (see Investigational Product Dosage below for specific dosage and schedule). • One of the three groups will follow the same schedule as the above two groups but with half of the doses of albumin alone (without IVIG), that is, 12 plasmaphereses with half-dose albumin alone. 
Patients in the control group will undergo sham procedures mimicking plasmaphereses but with neither fluid exchange nor albumin or IVIG administrations.
 | |
| CLINICAL STUDY DESIGN AND DESCRIPTION | A multicenter, randomized, controlled, parallel-group study | |
| POPULATION SIZE AND GROUPS | 
364 subjects with probable mild to moderate AD (NINCDS-ADRDA criterion; McKhann, et al. 1984.) and Mini-mental Status Examination (MMSE) score between ≥ 18 and ≤ 26.
 
There will be sites in Spain and USA.
 
The site of the Coordinating Investigator (Fundació ACE/Hospital Vall d'Hebron, Barcelona, SPAIN) will be the first site to be included. The rest of the sites will be incorporated progressively after the first site. Several months can elapse between the inclusion of the Spanish sites and the rest of sites.
 | |

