control patients. However, according to Version 1.0, laboratory values have only been assessed at Baseline, the intermediate visit, LVPE4, LVPE7, LVPE10, and the final Visit. The data from all protocols will be combined for the final analysis wherever possible. These study patients treated under protocol Version 1.0 will be combined to the treatment groups from protocol Version 2.0 or later versions of the protocol as follows:

- Treatment arm A: (100% albumin+Flebo V1.0) + (100% albumin+Flebo V2.0)
- Treatment arm B: (1/2 albumin+Flebo V1.0) + (1/3 albumin+Flebo V1.0) + (1/2 albumin+Flebo V2.0)
- Treatment arm C: (1/2 albumin V2.0)
- Treatment arm D (no treatment): (Control V1.0) + (Sham V2.0)

where V2.0 is protocol Version 2.0 or later versions.

A sample size of 312 subjects (78 per each of the 4 groups) will make it possible to detect with nearly 92% power for the first of the co-primary efficacy variables (the changes from baseline of the ADAS Cog scores) a difference in the mean of 3 points between any of the treatment groups and the control group, assuming the common standard deviation (SD) to be 5.55 (according to the data obtained in the phase II study), with a level of significance of 5%. This same sample size provides over 98% power for second of the co-primary end point variables (the changes from baseline of the ADCS-ADL scores) a difference in the mean of 6.69 points between any of the treatment groups and the control group, assuming the common standard deviation (SD) to be 10.0 (according to the data obtained in the phase II study), with a level of significance of 5%.

The study will have joint power for these co-primary end points of at least 90% ($0.92 \times 0.98 = 0.90$). The calculation makes the conservative assumption that these end points are independent. Since these end points are positively correlated 90% should serve as a lower bound on power.

Assuming a global dropout rate of approximately 15%, the study would have to enroll 364 subjects to obtain 312 subjects for evaluation.

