4.2 STATISTICAL DECISION RULES

The statistical tests will be performed with a 5% significance level and will be two-sided. In addition to the tests, two-sided 95% confidence intervals (95% CI) will be reported.

Because the end points are co-primaries, both must be statistically significant for the study to provide evidence of efficacy. Therefore, no multiplicity adjustment is needed to adjust for the co-primary end points. However, to account for the three dose group comparisons to placebo and to maintain the overall significance level of 0.05, adjustment for α will be made for multiple dose groups according to the Hochberg¹ procedure. The

	Title: Statistical Analysis Plan
	Project #: IG1002 AMBAR
	Version: Final 1.0 Effective Date: 31July2018
	Protocol Version: Version 5.0 Effective Date: Feb2018

Hochberg procedure will be implemented as follows: For each end point, the three dose group comparisons versus placebo will be ordered according to the p-value from the largest to the smallest. If the largest p-value is < 0.05 then all comparisons to placebo will be declared significant. Otherwise, if the second largest p-value is < 0.025 (0.05/2) then this dose and all doses with smaller p-values will be declared significant. Otherwise, if the smallest p-value is < 0.0167 (0.05/3) then this dose will be declared significant. Otherwise, no dose is considered significantly different from placebo. This procedure has been demonstrated to control the overall Type I error at 0.05. Both co-primary end points must be significant at a given dose to provide evidence of efficacy for that dose.

Specifically, the null hypothesis for all inferential analyses, including the primary end points, is that all three treatment groups are equal to placebo. Specific doses will be considered different from placebo if statistically significant following the Hochberg procedure described above. The study is considered positive if at least one dose group differs from placebo in both of the co-primary analyses. Subsequently, secondary end points are considered positive if at least one dose group differs from placebo.

A supportive analysis will be performed in per protocol analysis set for each of the co-primary efficacy end points applying the same respective methodologies, but without adjusting for Type I error.

[figure not shown]

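### The 90% joint power is not a lower bound: it leaves out the three-dose Hochberg adjustment, and a single effective dose has about 80% power

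*Protocol*

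**What the plan says.** Protocol 4.3 bases the sample size on "A sample size of 312 subjects (78 per each of the 4 groups"). For ADAS-Cog it takes "a difference in the mean of 3 points between any of the treatment groups and the control group" with an SD of 5.55 and reports nearly 92% power. For ADCS-ADL it takes "a difference in the mean of 6.69 points between any of the treatment groups and the control group" with an SD of 10.0 and reports over 98%. Both use a 5% significance level. The two are multiplied to 0.90 on the argument that treating the endpoints as independent is conservative, and the section concludes: "Since these endpoints may be positively correlated 90% should serve as a lower bound on power".

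SAP 2.1 carries the same calculation with a firmer premise: "Since these end points are positively correlated 90% should serve as a lower bound on power".

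The decision rule is set out in Protocol 10.2.2 and SAP 4.2. On each endpoint the three dose-versus-control p-values go through Hochberg with thresholds 0.05, 0.025 and 0.0167. The last step in the SAP reads: "Otherwise, if the smallest p-value is < 0.0167 (0.05/3) then this dose will be declared significant". A dose counts as effective only if both co-primary endpoints are significant for it, and under SAP 4.2 the study is positive if at least one dose meets that standard. Neither document brings these thresholds into the power calculation.

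**The concern.** The power figures and the decision rule use different significance levels. The only argument offered for calling 90% a lower bound concerns the correlation between the two endpoints. It does not address the correction for three doses, which lowers power whatever that correlation is.

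The sentence is the headline justification for the sample size in both documents. If 90% is believed to be a floor, a negative result will be taken as stronger evidence against every dose than the design can supply.

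**Working it through.** **Inputs.** Protocol 4.3: n = 78 evaluable per arm; difference 3 with SD 5.55; difference 6.69 with SD 10.0. Allocation is 1:1:1:1 and tests are two-sided (Protocol synopsis and 10.2.1). Thresholds are from SAP 4.2. The documents give no endpoint correlation, so 0 to 0.7 was assumed.

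**Formula.** Standardised difference δ = Δ / (SD × √(2/n)); power ≈ Φ(δ − z), where z is the two-sided critical value.

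- ADAS-Cog: δ = 3 / (5.55 × √(2/78)) = 3.376
- ADCS-ADL: δ = 6.69 / (10 × √(2/78)) = 4.178

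**Step 1: reproduce the plan.** At α = 0.05, z = 1.960.

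- Normal approximation: 92.2% and 98.7%; product 90.9%.
- Noncentral t, 154 df: 91.8% and 98.6%; product 90.5%.

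These match the stated figures, so the plan used two-sided 5% with no multiplicity adjustment. A one-sided 5% test would give 95.8% for ADAS-Cog.

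**Step 2: the threshold for a dose effective on its own.** The two null doses rarely give p-values small enough to open the 0.05 or 0.025 step, so the working threshold is usually 0.05/3, with z = 2.394.

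- Normal approximation: Φ(0.982) = 83.7% and Φ(1.784) = 96.3%; product 80.6%.
- Noncentral t, 154 df: 82.9% and 96.0%; product 79.5%.

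**Step 3: the full rule by simulation.** 1,000,000 replicates per scenario, normal test statistics, shared control arm, Hochberg run separately on each endpoint, both endpoints required at the same dose. Ranges cover correlations 0 to 0.7.

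| Doses with the full assumed effect | Joint power, a given effective dose | Joint power, at least one dose |
|---|---|---|
| One (other two null) | 80.9–83.1% | 80.9–83.4% |
| One (other two at half the effect) | 81.6–83.7% | 82.1–84.5% |
| Two (third null) | 84.3–85.9% | 93.0–93.7% |
| Three | 89.0–89.9% | 96.5–96.7% |

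**Step 4: can correlation rescue the bound?** No. With one effective dose, joint power cannot exceed the power on ADAS-Cog alone, which is about 84% even if the endpoints are perfectly correlated.

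**The case against.** **The 90% describes the study, and the study needs only one positive dose.** The phrase about any treatment group belongs to the separate endpoint figures, while the joint figure is attributed to the study. On that reading the claim is met when two or three doses have the full effect (about 93% and 96%). This limits the criticism to certain scenarios but does not save the bound: if one dose works, study power is that dose's power, about 81–83%, and it is still only 82–84% if the other two have half the effect.

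**One full effect and two nulls is an extreme case.** All three active arms share the same six-week intensive phase, and arms 2 and 3 differ only at the three IVIG sessions, so related effects are plausible. That is fair, and it is why the range of scenarios should be reported. Protocol 4.3, however, does not assume that all doses work. With the other two arms at three-quarters of the effect, simulated study power is about 89–90%, so shared benefit has to be substantial before 90% is reached.

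**The primary analysis is a covariate-adjusted MMRM** (SAP 7.4 and 9.1.1), which may be more precise than a two-sample comparison. This stands as a caveat. If covariates explained 10%, 15% or 20% of the variance on both endpoints (assumed values), simulated lone-dose joint power would be about 86–87%, 89% or 91%. The documents neither quantify such a gain nor use it to support the 90%.

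**The harm is limited**, because no analysis or error control changes and 95% confidence intervals will show what a negative result excludes. That is true, and it is why a wording correction suffices.

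**Conclusion.** The concern holds. The 90% is the joint power of a single dose comparison without multiplicity adjustment, and the planned test does not guarantee it. With one effective dose, joint power is about 80–81% under the plan's own independence assumption and about 83% at correlation 0.7. The chance of missing that dose is therefore about 17–20%, against the 10% the text implies. Power for a given dose falls just short of 90% even when all three doses work equally well. The figure is exceeded only for at least one positive dose when two or more doses have the full, or nearly the full, assumed effect.

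These results rest on the plan's own differences, SDs and 78 evaluable per arm, an unadjusted two-sample comparison, and assumed endpoint correlations of 0 to 0.7.

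**What to change.** Replace the lower-bound sentence in Protocol 4.3 and SAP 2.1 with a statement by scenario, for example: *Under the Hochberg rule, with both endpoints required at the same dose, joint power is about 80% if one dose is effective, about 84% per dose if two are, and about 89% per dose if three are. Power for at least one dose is about 93% and 96% in the last two cases. These figures use an unadjusted two-sample comparison and independent endpoints; any gain from covariate adjustment is not included.*

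The cost is wording only, and the stated power becomes less favourable. No change to the sample size, significance level or decision rule is requested. For scale, 90% joint power at 0.0167 under the same assumptions would need 96 evaluable per arm (4 × 96 = 384; 384 / 0.85 ≈ 452 enrolled).
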